Medication (Record Generic or trade name)	Reason for use (Medical History diagnosis or other reason, e.g. Prophylaxis)	Dose and units	Frequency	Route	Start Date (DD/MMM/YYYY)	Stop Date (DD//MMM/YYY)	Or tick if ongoing
1.					//	I	
2.					//	//	
3.					//	//	
4.					/	/	
5.							
6.							
7.					I		
PI signature			·	Date: _	•	·	

CONFIDENTIAL

[figure not shown]
Patient's Nº:				
---------------	--	--	--	--

[figure not shown]

Adverse Events (1/2)

AE No	Event Name (Please give Diagnosis if known)	Start date (DD/MMM/YYYY)	Stop date (DD/MMM/YYYY)	Serious?	comitant Medication	Severity 0 - Mild 1- Mode- rate 2 - Severe	Study Drug Action 0 - None 1 - Temporarily Interrupted 2 - permanently withdrawn	Outcome 1- Death related to AE 2- Not resolved/Not recovered 3- Resolved/ Recovered 4- Resolved/ Recovered with Sequelae 5- Resolving/ Recovering 6- Unknown	Relationship to Study Drug 0 - Certain 1 – Probable/Likely 2 - Possible 3 - Unlikely 4 – Conditional/ Unclassified 5 - Un-assessable/ Unclassifiable
				🗌 No	🗌 No				
1		//	//	🗌 Yes	Yes				
				🗌 No	🗌 No				
2		//	//	🗌 Yes	Yes				
				🗌 No	🗌 No				
3		//	//	🗌 Yes	Yes				
				🗌 No	🗌 No				
4		//	//	🗌 Yes	Yes				
				🗌 No	🗌 No				
5		//	//	🗌 Yes	Yes				
	I have reviewed the A knowledge, it accurat					ısality, se∖	verity and ou	Itcome and confirm	that, to the best of my
	PI signature				Date:				

Patient's N°:

Adverse Events (2/2)

AE No	Event Name (Please give Diagnosis if known)	Start date (DD/MMM/YYYY)	Stop date (DD/MMM/YYYY)	Serious?	Con- comitant Medication given	Severity 0 - Mild 1- Mode- rate 2 - Severe	Study Drug Action 0 - None 1 - Temporarily Interrupted 2 - permanently withdrawn	Outcome 1- Death related to AE 2- Not resolved/Not recovered 3- Resolved/ Recovered 4- Resolved/ Recovered with Sequelae 5- Resolving/ Recovering 6- Unknown	Relationship to Study Drug 0 - Certain 1 – Probable/Likely 2 - Possible 3 - Unlikely 4 – Conditional/ Unclassified 5 - Un-assessable/ Unclassifiable
				🗌 No	🗌 No				
1		//	//	Yes	🗌 Yes				
				🗌 No	🗌 No				
2		//	//	C Yes	🗌 Yes				
				🗌 No	🗌 No				
3		//	//	🗌 Yes	🗌 Yes				
				🗌 No	🗌 No				
4		//	//	🗌 Yes	🗌 Yes				
				🗌 No	🗌 No				
5		//	//	🗌 Yes	🗌 Yes				
	I have reviewed the knowledge, it accura					usality, sev	verity and ou	tcome and confirm	hat, to the best of my
	PI signature				Date:				

Patient's Nº:		Patient's Initials:			Unscheduled Visit
				-	

Date of Unscheduled Visit: / /

____ (DD / MMM / YYYY)

Vital Signs

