Vital Signs & Weight:

Weight: _____ Kg

Blood Pressure (Systolic/Diastolic): ____ / ___ mmHg

Physical Examination

*Please fill the relevant forms of adverse events in case any untoward or unusual event that occurred since last visit, whether it is believed to be related to the study drug or not.

Physical Examination	Normal	Abnormal	
Findings		 	

Is the participant taking any	No Yes		
concomitant medications?	If Yes: Complete Concomitant Medication		
conconnitant medications :	Page 26		

Is the participant had any Adverse Events

The investigator shall ask probing questions, allowing the patient to tell about any untoward or unusual event that occurred since the last visit, whether he/she (the patient) believes it is related to the study drug or not? (including abnormal physical examination/ laboratory results)		Complete 30
---	--	-------------

I have updated the AEs on page And have assessed them for seriousness, causality, severity and outcome and confirm that, to the best of my knowledge, it accurately reflects the study information obtained for this participant:

Investigator's Name:

Investigator's Signature: _____ Date: ____/ ____/

(DD / MMM / YYYY)	
-------------------	--

Patient's Nº:			Patient's Initials:			Study Completion page
Study Completion						
Did participant	complete	the trial?				
Yes, Please pro	ovide date of	f last day:				
/ / 2 0 (DD / MMM / YYYY)						
No, Please provide date of withdrawal and complete below:						
/	/20		(DD / I	MMM / YYY	Y)	
Early Withdrawa trial:	al: please	tick mos	t appropriate r	eason for p	particip	ant not completing the
Adverse Events related: please state related AE:(add details to AE page)						
Participant's decision, specify:						
☐ Investigator's decision, specify:						
Sponsor's decision						
□ Lost to follow up						
Patient deceased						
☐ Ineligibility (either arising during the study or retrospective having been overlooked at screening)						
Significant protocol deviation						
Significant non-compliance with treatment regimen or study requirements						
Disease progression which requires discontinuation of the study medication or results in inability to continue to comply with study procedures						
Consent with	hdrawn.					
Pregnancy or discontinuation of contraception						
Other, specify:						
Investigator Sig	jn off					
Investigator's N	lame:					
Investigator's S	ignature:				 D / MMM ;

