- Improvement in Patients' quality of life (QoL) between 3 treatment groups after 3 months (visit 4) and 6 months of treatment (End of Study visit), using The RAND 36-Item Health Survey such as:
 - Physical functioning,
 - Role limitations due to physical health,
 - Role limitations due to emotional problems,
 - Energy/fatigue,
 - Emotional well-being, social functioning,
 - o Pain
 - General health
- Incidence of serious/non-serious adverse events, including changes in lab tests
- AEs leading to permanent discontinuation of the study drug.

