11.2 Analysis populations

Analysis of all efficacy variables will be performed only for patients who completed the study without protocol violation (as per protocol).

Analysis of all safety variables will be performed for all patients (intent-to-treat population) who received even 1 dose of the treatment; either Ursoplus[®] capsules or UDCA or Placebo.

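### The Study Completion page merges stopping study drug with leaving the trial, and efficacy is analysed in completers only, so the arm comparison is at risk of bias of unknown direction

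*Protocol*

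**What the plan says.** The document supplied as the protocol is a case report form (CRF). Its Study Completion page asks one question, whether the participant finished the trial. The negative answer reads "No, Please provide date of withdrawal and complete below" and leads to a list of early-withdrawal reasons. Two of these describe, wholly or partly, the end of treatment rather than the end of follow-up: "Disease progression which requires discontinuation of the study medication or results in inability to continue to comply with study procedures" and "Significant non-compliance with treatment regimen or study requirements".

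Elsewhere the documents treat the end of treatment as an event of its own. The Adverse Events log has a study-drug action code, "2 - permanently withdrawn", and SAP 5.2 lists "AEs leading to permanent discontinuation of the study drug" as a secondary endpoint.

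SAP 5.1 places the primary endpoint (total and direct bilirubin, ALT, AST, ALP, GGT) at the End of Study visit. SAP 11.2 sets the efficacy population: "Analysis of all efficacy variables will be performed only for patients who completed the study without protocol violation (as per protocol". The wider population, everyone with at least one dose, is used for safety variables only. SAP 11.3 names no method for missing values. SAP section 9 confirms that the trial is open label.

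**The concern.** Stopping a drug and leaving a trial are different events. A patient can do the first and still give blood at week 24. When one tick box serves for both, a site may close a patient's follow-up because treatment ended, and the record cannot show afterwards which of the two happened. The progression box makes this plain, since it joins stopping medication and inability to follow procedures with an alternative.

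Here the loss would be complete. With no scheduled laboratory value between baseline and week 24, neither a repeated-measures model nor a last post-baseline value has anything to work with. Because arm and patient are unblinded, the decision to stop or leave may differ between arms. What is at stake is the randomised comparison on all six primary laboratory variables, on steatosis and on the week-24 quality-of-life scores.

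**Working it through.** **1. Where the efficacy outcomes are collected (CRF)**

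| Form | Liver tests | FibroScan | RAND-36 |
|---|---|---|---|
| Screening | yes | yes | yes |
| Visits 2, 3, 5, 6 (weeks 4, 8, 16, 20; may be by phone) | no | no | no |
| Visit 4 (week 12) | no | no | yes |
| End of Study (week 24) | yes | yes | yes |
| Unscheduled visit | no | no | no |

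There is no early-termination form. A patient recorded as withdrawn before week 24 has no scheduled post-baseline liver test or FibroScan, and SAP 11.2 would exclude the patient from efficacy in any case.

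**2. The plan's own figure (SAP section 7)**

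The changes in total bilirubin in the cited study are:
- placebo 1.8 − 1.6 = +0.2
- UDCA 1.2 − 1.3 = −0.1
- combination 1.2 − 1.4 = −0.2

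I take the unit as mg/dl, as in the eligibility criteria. The standard deviation of the three means (divisor 3) is 0.16997. Dividing by 0.8 gives 0.21246, the stated f, so the implied SD is 0.8. That value is back-calculated and does not appear in the SAP.

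λ = f²N = 0.2124591² × 270 = 12.187, and the critical F on 2 and 267 df is 3.030. Both match the SAP. Power comes to 0.885 against the stated 0.870. The gap of 1.5 points does not affect this point. The planned placebo minus Ursoplus difference is 0.2 − (−0.2) = 0.40 mg/dl.

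**3. Illustration: loss driven by a marker of bilirubin rise**

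Assumptions: change is normal with the means above, σ = 0.8, 99 per arm. A patient leaves when a marker with the same distribution exceeds c = 1.2 mg/dl. The marker has correlation ρ with the week-24 change.

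With z = (c − μ)/σ, the proportion leaving is 1 − Φ(z). The mean change among those who stay is μ − ρσφ(z)/Φ(z).

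| Arm | z | Leaving | Shift in mean |
|---|---|---|---|
| Ursoplus | 1.750 | 4.0% | −0.072ρ |
| UDCA | 1.625 | 5.2% | −0.090ρ |
| Placebo | 1.250 | 10.6% | −0.163ρ |

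Overall loss is (4.0 + 5.2 + 10.6)/3 = 6.6%, about 20 of 297, which is inside the 10% dropout allowance. The observed difference is 0.40 − (0.163 − 0.072)ρ. Power is for the one-way ANOVA, by simulation.

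| ρ | Difference (mg/dl) | Power |
|---|---|---|
| 1 (perfect selection) | 0.31 | 0.78 to 0.79 |
| 0.5 to 0.3 | 0.35 to 0.37 | 0.82 to 0.85 |
| 0 (unrelated to outcome) | 0.40 | 0.89 |

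The fair reference for power is 0.885 at the plan's 270 evaluable patients. At ρ = 1, a cut-off of 1.0 gives 0.28 (10.3% loss) and a cut-off of 1.5 gives 0.34 (3.1% loss).

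**4. Direction**

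Suppose instead that a share q of each arm leaves and leavers are D mg/dl worse than those who stay. The difference is then 0.40 − D(q_placebo − q_Ursoplus).

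| Loss, placebo / Ursoplus | D = 0.25 | D = 0.5 | D = 1.0 | Exactly the worst patients leave |
|---|---|---|---|---|
| 10% / 10% | 0.40 | 0.40 | 0.40 | 0.40 |
| 15% / 5% | 0.375 | 0.35 | 0.30 | 0.27 |
| 5% / 15% | 0.425 | 0.45 | 0.50 | 0.53 |

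The planned Ursoplus-UDCA difference is only −0.1 − (−0.2) = 0.10. In the last column's setting it runs from −0.03 (15% UDCA / 5% Ursoplus) to 0.23 (reverse). With no true effect and losses of 15%, 10% and 5%, the ANOVA's rejection rate is 0.053, 0.063 and 0.105 for D = 0.25, 0.5 and 1.0.

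**The case against.** The strongest reply is that the page is only a menu of reasons for patients who have left. No text says that a patient who stops drug must leave. The adverse event log codes drug withdrawal separately, and the week-24 form is not conditional on being on drug. A patient off drug could attend week 24 and be marked as having finished. The supplied document is also a CRF, so a protocol body may contain follow-up rules not seen here. All of this stands. A reader might infer that these outcomes are never collected, and the documents do not support that. They show only that nothing supplied provides for collection once a patient is recorded as withdrawn.

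A reader might also infer that the arm difference is biased, and towards no effect, because the worst placebo patients leave. That is not shown either. The documents give no dropout by arm or by reason. Loss that is equal and equally selective gives no bias in this model, and the sign can go either way. Nor do the documents say that non-compliant patients do worst. Perfect selection on the week-24 bilirubin is hard to credit when no bilirubin is scheduled between baseline and week 24, so 0.31 is the extreme for that cut-off and not an estimate.

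The illustration also uses absolute change pooled over strata, whereas SAP 11.4.1 analyses percent change and the table shells report each fibrosis stratum separately.

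Finally, "Sponsor's decision" has no line for details, which may look like a unique gap. It is not: the boxes for protocol deviation and non-compliance also need judgement and have none.

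What survives is the merged record, the absence of any provision for off-drug week-24 data, and an efficacy set that would discard such data even if they were obtained.

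**Conclusion.** The point holds as a risk and not as a demonstrated bias. Followed as written, the plan drops patients recorded as withdrawn after stopping drug from the primary comparison, with no scheduled post-baseline laboratory value to fall back on.

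Under the assumptions in the working (section 7 changes, SD 0.8 inferred from f, a 1.2 mg/dl marker, about 7% loss), the planned 0.40 mg/dl becomes 0.35 to 0.37 at moderate correlation. It is 0.31 at the extreme and 0.40 if loss is unrelated to outcome. With greater loss on active drug the difference is inflated instead. Direction and size cannot be fixed from the documents. The possible shift of 0.13 mg/dl either way in the worst-patient setting exceeds the 0.10 planned between Ursoplus and UDCA, so that contrast is the most exposed.

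The form and the analysis set act together. Splitting the page alone changes no efficacy result while SAP 11.2 stands. Changing the analysis set alone leaves the week-24 values missing. This should be corrected, since the remedy adds no procedure.

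**What to change.** 1. On the Study Completion page, record two separate items: (a) study drug stopped, with date and reason; (b) left the trial, with date and reason.
2. State that patients who stop drug and still consent keep the assessments already scheduled: RAND-36 at visit 4, and liver tests, FibroScan and RAND-36 at week 24.
3. Amend SAP 11.2 so that these values enter an efficacy analysis of all randomised patients by assigned arm, with the per-protocol analysis kept as supportive. Name a method, with a sensitivity analysis, for values that are still missing.

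The rules for when drug is stopped are unchanged. The cost is one CRF page and a short SAP amendment. The downside is some follow-up of patients off drug, and an estimate that includes off-drug time.

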2 STUDY DESIGN

This is a Prospective, Multi center, open-label, randomized, control, Interventional, phase IV Study will be conducted in 2 sites in Egypt; the Research Center of Air Force Specialized Hospital and Helwan University Hospital to assess the efficacy & safety of Ursoplus® capsules (UDCA 250mg & Silymarin 140mg) versus UDCA alone versus Placebo among compensated Chronic Liver Disease Patients.

This study is a clinical trial that will enroll 297 patients, based on Vibration-controlled transient elastography in screening visit; subjects will be enrolled in 2 groups:

- Group 1: with non-cirrhosis, F0, F1 and F2.
- Group 2: with advanced fibrosis and cirrhosis, F3 and F4

Subjects in each group (1 or 2) will be treated with either:

- Ursoplus[®] capsules (group A),
- Ursofalk® capsules (UDCA 250mg); group B (control group 1):
- Or with Placebo, in group C (control group 2), using Stratified random sampling

Generated by Data Management department (DM) of the CRO (Nagy Research) for the 3 treatment groups with a ratio of 1: 1:1. Subjects who will be enrolled in this study will agree to the release of information and sign an informed consent. Subjects included in this study are enrolled for the collection of data that reflect the care they receive under routine clinical circumstances. All provided care should be according to protocol and the local standard of medical care.

The screening and enrollment period is planned to be 6 months. The total duration of the study/subject will be 6 months for treatment, follow-up, and End of Study visits

3 Inclusion and Exclusion Criteria:

3.1 Inclusion Criteria:

Subjects meeting all of the following criteria will be considered for enrollment in the study:

- 1. Male and female patients aged ≥ 18
- 2. Subjects with Compensated Chronic Liver Disease, defined as child 5-7.
- 3. Patients with mild disturbance of liver biochemical profile by one of the following criteria: (elevated Total Serum Bilirubin ≤ 3 mg/dl, or elevated Direct Serum Bilirubin ≤ 2 mg/dl, or elevated one or more of liver enzymes up to 3 times of the normal level).: (Alanine Transaminase (ALT), Aspartate Aminotransferase (AST), Alkaline Phosphatase (AIP) & Gamma Glutamyl Transpeptidase (GGT)).
- 4. Non-diabetic subjects and subjects with Controlled DM-type 1 and 2 patients, HbA1C up to 7.5%
- 5. Non-pregnant or lactating female patients
- 6. Subjects who are willing to sign Informed Consent Form and ready to comply with the protocol for the duration of the study

3.2 Exclusion Criteria:

Subjects presenting with any of the following will not be included in the study:

- 1. Subjects with a history of hypersensitivity to any of the ingredients of the medication being studied
- 2. Subjects with positive PCR or positive antibodies to hepatitis C in the past 6 months
- 3. Subjects with positive Hepatitis B surface antigen (HBsAg)

- 4. Subjects with elevated liver enzymes more than 3 times of the normal level Alanine Transaminase (ALT), Aspartate Aminotransferase (AST), Alkaline Phosphatase (ALP) & Gamma Glutamyl Transpeptidase (GGT).
- 5. Subjects with Primary Biliary Cirrhosis (PBC) and Primary Sclerosing Cholangitis (PSC).
- 6. Subjects with Child Pugh Score more than 7
- 7. Subjects with history of bleeding varices, as sign of decompensated liver.
- 8. Subjects having uncontrolled Diabetes (HBA1C above 7.5 %)
- Subjects with any medical condition requiring the usage of medication that may interfere with the absorption, distribution, metabolism or excretion of the study drug such as the followings:
 - a. Bile acid sequestering agents such as cholestyramine and colestipol,
 - b. Antacids containing aluminum hydroxide.
 - c. Drugs affecting lipid metabolism such as estrogens, oral and hormonal contraceptives, and clofibrate (and perhaps other lipid-lowering drugs)
- 10. Subjects who are receiving other liver support drugs (including drugs of the study), 1 month before study initiation.
- 11. Subjects with auto immune liver disease taking corticosteroid or immune suppressant
- 12. Pregnant or breast-feeding women
- 13. Use of oral contraceptives in child bearing ladies

4 Medicinal Products:

- Ursoplus[®] capsules (UDCA 250mg & Silymarin 140mg)
- Ursofalk® capsules (UDCA 250mg)
- Placebo

5 Endpoints:

5.1 Primary Efficacy Endpoints:

 Change in Liver Function Tests including; Total serum bilirubin, Direct Serum Bilirubin, and elevated Liver Enzymes (ALT, AST, ALP & GGT) between 3 treatment groups after 6 months of treatment (End of Study visit)

5.2 Secondary Endpoints:

- Change in degree of Steatosis from baseline (visit 1) to End of study between 3 treatment groups, measured by Vibration-controlled transient elastography with CAP.
- Improvement in Patients' quality of life (QoL) between 3 treatment groups after 3 months (visit 4) and 6 months of treatment (End of Study visit), using The RAND 36-Item Health Survey such as:
 - Physical functioning,
 - Role limitations due to physical health,
 - Role limitations due to emotional problems,
 - Energy/fatigue,
 - Emotional well-being, social functioning,
 - o Pain
 - General health
- Incidence of serious/non-serious adverse events, including changes in lab tests
- AEs leading to permanent discontinuation of the study drug.

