Spleen	Normal		Abnormal			
lf abnormal,						
findings:	Splenic Vein Diameter:mm					
Gall Bladder	Normal		Abnormal			
lf abnormal,						
findings:	Common B	ile Duct (CBD) Diame	ter:mm (Ν. ι	ıp to 6mm)		

Patient's		Patient's	Screening Visit
Nº:		Initials:	Initiation Visit

Vibration-controlled transient elastography with CAP (Fibroscan)

Date of Fibroscan: ___/ ___/ (DD / MMM / YYYY)

	Liver stiffness measurement	Fi	broscan score	
Liver		F0/F1	F2	
		F3	F4	
If abnormal, findings:				
Safety Laboratory Tests				

Date of Laboratory Tests: __/ __/ (DD / MMM / YYYY)

Laboratory Parameter	Value	Unit	If parameter indicated as out of normal range on report, please check if clinically significant:
ALT			🗌 No 🔄 Yes
AST			□ No □ Yes
Alkaline Phosphatase (ALP)			□ No □ Yes
Gamma-GT			□ No □ Yes
Total Bilirubin			□ No □ Yes
Direct bilirubin			□ No □ Yes
S Albumin			□ No □ Yes
РТ			□ No □ Yes
HbA1c for diabetic patients			□ No □ Yes
PCR/ Antibody for hepatitis C			□ No □ Yes
HBs Ag			□ No □ Yes
Serum β -HCG (for Females in child bearing period)			□ No □ Yes

Patient's		Patient's		Screening Visit
Nº:		Initials:		Initiation Visit

Assessment for quality of life (The RAND 36-Item Health Survey)

Completed

Not Completed

End of Screening Visit

End	of Screening Visit Checklist:	Yes	No
1.	Does the participant meet the inclusion and exclusion criteria to date?		
2.	Have all Screening Visit procedures been completed?		
3.	Have the Medical History and Concomitant Medication pages been completed?		

Participant's eligibility:
Is the participant eligible to take part in the Clinical Study?
☐ Yes
□ No, Please give reason for screen failure below
Reason(s) for screen failure:
1.
2.
Investigator Sign-Off
Investigator's Name:
Investigator's Signature: Date ://
(DD / MMM / YYYY)

Patient's Nº:		Patient's Initials:		Scre Initi	ening Visit ation Visit		
	Randomization						
Group A	A	Group B		Group C			
			·				
Drug Dispense							

Date of Drug Dispense: ___/ ___ (DD / MMM / YYYY)

Drugs are dispensed for the patient to be sufficient for 30 days of treatment The subject is asked to take the treatment daily and come next visit with the empty blisters after 30 days, with a window of 7 days.

Drug Dispense	Number of Capsules	Number of Blisters
Drug A, B, or C		

Investigator's Name:

Investigator's Signature: _____ Date: ___/ ___/

(DD / MMM / YYYY)

Visit 2 (Week 4) (may be done by phone call)

Date of Visit 2: ___/ ___ (DD / MMM / YYYY)

Vital Signs

Vital Signs & Weight:

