Is the participant taking any concomitant medications?	No Yes If Yes: Complete Concomitant Medication
	Page 26

Is the participant had any Adverse Events

I have updated the AEs on page And have assessed them for seriousness, causality, severity and outcome and confirm that, to the best of my knowledge, it accurately reflects the study information obtained for this participant:

Investigator's Name:

Investigator's Signature: _____ Date: ___/ ___/

(DD / MMM / YYYY)

Patient's Nº:		Patient' s Initials:			Visit 4 (Week 12) Follow Up Visit 3
		initiais:			•

Visit 4 (Week 12)

Date of Visit 4: ___/ ___/ (DD / MMM / YYYY)

Vital Signs

Vital Signs & Weight:

Weight: _____ Kg

Blood Pressure (Systolic/Diastolic): ____ / ___ mmHg

Physical Examination

*Please fill the relevant forms of adverse events in case any untoward or unusual event that occurred since last visit, whether it is believed to be related to the study drug or not.

Physical Examination	Normal	Abnormal	
Findings			

The RAND 36-Item Health Survey				
Completed		Not Completed		

Patient's Nº:		Patient' s		Visit 4 (Week 12) Follow Up Visit 3
		Initials:		

Drug Dispense

 Date of Drug Dispense:
 /
 /
 (DD / MMM / YYYY)

Drug Dispense	Number of Capsules	Number of Blisters
Drug A, B, or C		

Drugs are dispensed for the patient to be sufficient for 30 days of treatment The subject is asked to take the treatment daily and come next visit with the empty blisters after 30 days, with a window of 7 days.

Is the participant taking any	🗌 No 🔄 Yes		
concomitant medications?	If Yes: Complete Concomitant Medication		
	Page 26		

Is the participant had any Adverse Events

I have updated the AEs on page And have assessed them for seriousness, causality, severity and outcome and confirm that, to the best of my knowledge, it accurately reflects the study information obtained for this participant:

Investigator's Name: _____

Investigator's Signature: _____ Date: ___/ ___/

(DD / MMM / YYYY)

Patient' s Initials:

als:

Visit 5 (Week 16) (may be done by phone call)

Date of Visit 5: ___/ ___ (DD / MMM / YYYY)

Vital Signs

Vital Signs & Weight:

Weight: ____ Kg

Blood Pressure (Systolic/Diastolic): _____ / ____ mmHg

Physical Examination

[figure not shown]
*Please fill the relevant forms of adverse events in case any untoward or unusual event that occurred since last visit, whether it is believed to be related to the study drug or not.

Physical Examination	Normal	Abnormal	
Findings		 	

Drug Dispense

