11.4.1 Primary analysis

A. Percent change in Liver Function Tests including; Total serum bilirubin, direct serum bilirubin and Elevated Liver Enzymes (ALT, AST, ALP & GGT) after 6 months of treatment.

11.4.2 Secondary analysis:

- A. Improved degree of Steatosis from baseline (visit 1) to End of study between 3 treatment groups
- B. Improved quality of life between 3 treatment groups after 3 months (visit 4) and 6 months of treatment (End of study visit), using the RAND 36-Item Health Survey such as:
 - Physical functioning,
 - Role limitations due to physical health,
 - o Role limitations due to emotional problems,
 - Energy/fatigue,
 - Emotional well-being, social functioning,
 - o Pain
 - General health.
- C. Serious Adverse Events (SAEs)
- D. Adverse Events (AEs), including changes in any lab tests.
- E. AEs leading to permanent discontinuation of the study drug.

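### Lab changes are a safety endpoint in all dosed patients, but patients who leave before week 24 have no scheduled or structured post-baseline lab values

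*SAP*

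**What the plan says.** **Endpoint.** SAP 5.2 includes "Incidence of serious/non-serious adverse events, including changes in lab tests" among the secondary endpoints. SAP 11.4.2 D repeats it as "Adverse Events (AEs), including changes in any lab tests". Adverse events (AEs) that lead to permanent discontinuation are a further endpoint in both places.

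**Population.** SAP 11.2 states: "Analysis of all safety variables will be performed for all patients (intent-to-treat population) who received even 1 dose of the treatment". The same section limits efficacy to patients who finish the study without a protocol violation.

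**Data collection.** The CRF has a block headed "Safety Laboratory Tests" on the screening pages and again on the End of Study (week 24) pages. The pages for Visits 2 to 6 have no such block. The Unscheduled Visit page covers weight, blood pressure, examination, concomitant medication and an AE question. The Study Completion page takes a date and a reason for withdrawal. The reasons include an AE and "Disease progression which requires discontinuation of the study medication or results in inability to continue to comply with study procedures".

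**Reporting.** SAP 12.3.3 has three table shells: AEs, serious AEs and concomitant medication. The lab analytes appear only in Tables 3 to 8, under the primary efficacy endpoint.

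**The concern.** The plan promises a lab-based safety result in all dosed patients, but the forms supply structured lab data mainly for those who reach week 24. Patients who leave earlier may do so because of an AE or worsening liver disease, and both are listed reasons for withdrawal. Missing lab values in this group may therefore be informative. If one arm loses more patients for liver-related reasons, the week-24 values would make that arm look better than it is. No planned table would show this, because no lab table covers the safety population and none counts missing lab values by arm.

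**Working it through.** **1. Where lab values are collected.** Each CRF page was read for lab fields.

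| CRF page | Lab block | Other route for a lab finding |
|---|---|---|
| Screening | Yes | Not needed |
| Visits 2, 3, 5, 6 (weeks 4, 8, 16, 20; may be by phone) | No | AE question |
| Visit 4 (week 12; not marked as a phone visit) | No | AE question |
| End of Study (week 24) | Yes | AE question |
| Unscheduled Visit | No | AE question, which names laboratory results |
| Study Completion | No | AE-related withdrawals are sent to the AE page |

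Seven analytes are on both the screening and week-24 panels: ALT, AST, ALP, GGT, albumin, total bilirubin and direct bilirubin. Change from baseline can be calculated for these in anyone who has the week-24 panel.

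**2. Where lab values are reported.** Tables 12 and 13 count AEs and serious AEs. Tables 3 to 8 report six of the seven analytes (albumin is not among them), but as efficacy outputs, which SAP 11.2 restricts to completers without violation. The second row in those shells is labelled V6. The CRF's Visit 6 is week 20 and has no lab block, so I read V6 as End of Study, in line with the six months in the table titles. On that reading, no shell tabulates lab values in all dosed patients.

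**3. How many patients are affected.** Inputs are from SAP 7: 270 evaluable, 10% drop-out, 297 in total, 1:1:1 allocation.

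- The plan's figure reproduces: 270 × 0.10 = 27, and 270 + 27 = 297.
- Share of those enrolled: 27 / 297 = 9.1%.
- Per arm: 27 / 3 = 9 of 99.
- If 10% is applied to the number enrolled instead: 297 × 0.10 = 29.7, about 30.
- Assumed drop-out range of 5% to 20%: 297 × 0.05 = 14.9 to 297 × 0.20 = 59.4, so about 15 to 59 patients.

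**4. What share of lab worsening could fall outside the panel.** The documents give no rate of lab worsening, so this is an illustration. Assume worsening in 5% of 270 completers: 270 × 0.05 = 13.5 cases on the week-24 panel. Let q be the rate among the 27 early leavers. The share of all cases outside the panel is 27q / (13.5 + 27q).

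| q (assumed) | Cases among early leavers | Share outside the panel |
|---|---|---|
| 5% (no informative loss) | 1.35 | 1.35 / 14.85 = 9% |
| 10% | 2.7 | 2.7 / 16.2 = 17% |
| 30% | 8.1 | 8.1 / 21.6 = 38% |
| 50% | 13.5 | 13.5 / 27 = 50% |

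These are shares outside the structured panel, not shares lost to the safety analysis. Some of these cases would be recorded as AEs.

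**The case against.** The strongest reply is that the endpoint is an incidence of AEs, and the CRF gives abnormal lab results a way in. The AE question explicitly covers laboratory results on the Unscheduled Visit page and on several scheduled pages, including End of Study. AE-related withdrawals are directed to the AE page. This is correct. A reader might infer that early leavers contribute no lab safety information at all, and the documents do not support that. They have baseline values, and a known abnormality can be counted. What remains is that this route depends on a test being ordered and judged abnormal, in an open-label trial, and provides no field for the value itself.

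A reader might also cut the safety denominator to completers. SAP 11.2 keeps it at all dosed patients. A patient who stops for a known abnormality should still be counted through the AE log.

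Stopping the drug is not shown to mean leaving the study. The AE log records permanent withdrawal of drug separately from the Study Completion page, and a patient off drug could still attend week 24. The point therefore concerns patients who leave the study.

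The protocol file is a CRF, its completion page is cut off at the signature, and no procedural text is available. An early-withdrawal visit may be described elsewhere. That limits confidence, but does not alter the absence of lab fields on the pages shown.

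Finally, a reader who sees that prothrombin time is not on the week-24 panel might call the missing end-of-study Child-Pugh score a defect. The documents use Child-Pugh for entry only, and no endpoint or table needs it later. Ascites and encephalopathy have no dedicated week-24 field either, so adding prothrombin time alone would not produce a structured score.

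**Conclusion.** The point holds for structured data. In the CRF shown, patients who leave the study before week 24 have no scheduled or structured post-baseline lab values. Their lab changes reach the safety analysis only if a test is done and reported as an AE. The lab part of the all-dosed safety analysis is therefore largely a completers' analysis, and no planned table reveals the gap.

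The size is about 27 of 297 patients, or 9 per arm. This treats the plan's drop-out allowance as the number of dosed patients who leave before week 24. The allowance is all-cause: it may include patients never dosed, and nothing shows how many would leave for liver-related reasons. The direction and size of any bias between arms cannot be derived from the documents.

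This should be changed because it is cheap to fix and values not collected at withdrawal generally cannot be recovered. Confidence is moderate, for the reason given about procedures not shown.

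**What to change.** 1. **Early withdrawal.** State that the existing End of Study page, including its lab block and AE question, is completed at withdrawal for any patient who leaves before week 24. If another document already requires this, refer to it in the SAP.
2. **Unscheduled visits.** Add fields for lab values and sample date, to be filled when results are obtained. List these separately from scheduled values and keep them out of the arm comparison. Testing prompted by suspicion in an open-label trial may differ by arm.
3. **SAP 12.3.3.** Add a lab change and shift table for all dosed patients, covering the seven analytes on both panels. Use the week-24 or early-withdrawal panel, identify which was used, and give the number missing by arm.

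**Cost.** CRF page edits, one table shell, and one standard panel brought forward in about 27 patients. Early-withdrawal values will come at differing exposure times, so the sample day should be shown. Some early leavers will refuse, so the gap narrows but does not close. The primary analysis is unaffected, since SAP 11.2 restricts efficacy to completers.
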